12 ANALYSIS OF THE OBJECTIVES

12.1 Primary objective

“To determine the efficacy of Tafamidis free acid 61 mg in ATTRv patients with neurologic involvement included in studies B3461045 and/or LTE (B3461045) in Spain through changes in the 12-month NIS scale”

Primary variable: Neuropathy Impairment Score (NIS).

NOTE: ATTRv patients are considered to be those who have indicated “Mutation” in the genotype (Data related to the disease at diagnosis).

See resolution of this objective in 10.3.1 (month 12).

Additionally, the results will be presented for the percentage of patients responding to treatment of the change at month 12 with respect to the initial value. The N and % of patients responding to treatment will be calculated, defining responder as:

- change at 12 months compared to the initial data <4p in NIS, patients who have obtained less than 4 points in the NIS in month 12

Patients who do not meet the previous condition will be considered non-responders. If complete data is not available, the value will be left as missing.

12.2 Secondary objectives

12.2.1 Secondary objective 1

“To determine the efficacy of Tafamidis 61 mg in ATTRv patients with neurologic involvement included in studies B3461045 and/or LTE (B3461045) in Spain using additional non-cardiac variables at 6, 12, 18, 24 and 36 months after the start of treatment”

NOTE: ATTRv patients are considered to be those who have indicated “Mutation” in the genotype (“Data related to the disease at diagnosis”).

Results will be presented in each month (6, 12, 18, 24 and 36) (see section 6.1 visit reassignment).

Secondary objective 1 [sic: 2] variables:

- NIS at 6, 18, 24 and 36 months (see section 10.3.1)
- NIS-LL (section 10.3.2), Norfolk QoL-DN (section 10.5.1), COMPASS-31 (section 10.5.3) and FAP-RODs (section 10.5.2), FAP (section 10.3.3)
- % of patients whose stage does not progress in the PND score (section 10.3.4). N and % of patients whose stage does not progress in the PND will also be obtained, referring to patients who do not change to higher stages compared to the start of treatment.
- % of treatment responders. N and % of responder patients will be calculated for this objective, with responder being defined as:
 - **NIS:** Results will be presented in each month, defining responder as:
 - change at 6 months from baseline <2p in NIS, patients who have achieved less than 2 points in the NIS.
 - change at 12 months from baseline <4p in NIS, patients who have achieved less than 4 points in the NIS.
 - change at 18 months from baseline <6p in NIS, patients who have achieved less than 6 points in the NIS.
 - change at 24 months from baseline <8p in NIS, patients who have achieved less than 8 points in the NIS.
 - change at 36 months from baseline <12p in NIS and, patients who have achieved less than 12 points in the NIS.

Patients who do not meet the previous condition in each month will be considered non-responders. If complete data is not available, the value will be left as missing.

- **NIS-LL:** Results will be presented in each month, defining responder as:
 - change at 6 months from baseline <1p in NIS-LL, patients who have achieved less than 1 point in the NIS-LL at Month 6.
 - change at 12 months from baseline <2p in NIS-LL, patients who have achieved less 2 points in the NIS-LL at Month 12.
 - change at 18 months from baseline <3p in NIS-LL, patients who have achieved less than 3 points in the NIS-LL at Month 18.
 - change at 24 months from baseline <4p in NIS-LL, patients who have achieved less than 4 points in the NIS-LL at Month 24.
 - change at 36 months from baseline (<12p in NIS and <6p in NIS-LL), patients who

have achieved less than 12 points in the NIS and simultaneously less than 6 points in the NIS-LL at Month 36.

Patients who do not meet the previous condition in each month will be considered non-responders. If complete data is not available, the value will be left as missing.

– **NIS and NIS-LL:** Results will be presented in each month, defining responder as:

- change at 6 months from baseline (<2p in NIS and <1p in NIS-LL), patients who have achieved less than 2 points in the NIS and simultaneously less than 1 point in the NIS-LL at Month 6.
- change at 12 months from baseline (<4p in NIS and <2p in NIS-LL), patients who have achieved less than 4 points in the NIS and simultaneously less than 2 points in the NIS-LL at Month 12.
- change at 18 months from baseline (<6p in NIS and <3p in NIS-LL), patients who have achieved less than 6 points in the NIS and simultaneously less than 3 points in the NIS-LL at Month 18.
- change at 24 months from baseline (<8p in NIS and <4p in NIS-LL), patients who have achieved less than 8 points in the NIS and simultaneously less than 4 points in the NIS-LL at Month 24.
- change at 36 months from baseline (<12p in NIS and <6p in NIS-LL), patients who have achieved less than 12 points in the NIS and simultaneously less than 6 points in the NIS-LL at Month 36.

In this case, patients who do not meet the previous two conditions in each month will be considered non-responders. If complete data is not available (NIS and NIS-LL), the value will be left as missing.

- R-R Range Variability (section 10.4)
- mBMI (section 10.2).
- Amplitude of the potentials measured in sural sensory and ulnar, tibial and peroneal motor NCS (section 10.4)

To the extent possible, parametric (paired t-test) or non-parametric (Wilcoxon) statistical tests will be performed, depending on the sample distribution, to study whether there are differences in the unit change rate for pre- and post-treatment previous numeric variables (total and subgroups).

12.2.2 Secondary objective 2

“To determine the efficacy of Tafamidis free acid 61 mg in ATTRwt patients with neurological symptoms included in studies B3461045 and/or LTE (B3461045) in Spain, through non-cardiac variables at 6, 12, 18, 24 and 36 months after treatment initiation.”

NOTE: ATTRwt patients are considered to be those who have indicated “Wildtype” in the genotype (“Data related to the disease at diagnosis”).

Results will be presented in each month (6, 12, 18, 24 and 36) (see section **Error! Reference source not found.** visit reassignment).

Secondary objective 1 [sic: 2] variables:

- NIS (see section 10.3.1), NIS-LL (section 10.3.2), Norfolk QoL-DN (section 10.5.1), COMPASS-31 (section 10.5.3) and FAP-RODs (section 10.5.2), FAP (section 10.3.3)
- % of patients whose stage does not progress in the PND score (section 10.3.4). N and % of patients whose stage does not progress in the PND will also be obtained, referring to patients who do not change to higher stages compared to the start of treatment.
- % of treatment responders. N and % of responder patients will be calculated for this objective, with responder being defined as:
 - change at 6 months from baseline (<2p in NIS and <1p in NIS-LL), patients who have achieved less than 2 points in the NIS and simultaneously less than 1 point in the NIS-LL at Month 6.
 - change at 12 months from baseline (<4p in NIS and <2p in NIS-LL), patients who have achieved less than 4 points in the NIS and simultaneously less than 2 points in the NIS-LL at Month 12.
 - change at 18 months from baseline (<6p in NIS and <3p in NIS-LL), patients who have achieved less than 6 points in the NIS and simultaneously less than 3 points in the NIS-LL at Month 18.
 - change at 24 months from baseline (<8p in NIS and <4p in NIS-LL), patients who have achieved less than 8 points in the NIS and simultaneously less than 4 points in the NIS-LL at Month 24.

- change at 36 months from baseline (<12p in NIS and <6p in NIS-LL), patients who have achieved less than 12 points in the NIS and simultaneously less than 6 points in the NIS-LL at Month 36.
- R-R Range Variability (section 10.4)
- mBMI (section 10.2).
- Amplitude of the potentials measured in sural sensory and ulnar, tibial and peroneal motor NCS (section 10.4)

To the extent possible, parametric (paired t-test) or non-parametric (Wilcoxon) statistical tests will be performed, depending on the sample distribution, to study whether there are differences in the unit change rate for pre- and post-treatment previous numeric variables (total and subgroups).

12.2.3 Secondary objective 3

“To describe the extra-cardiac characteristics of ATTRv and ATTRwt patients included in studies B3461045 and/or LTE (B3461045) in Spain with mixed phenotype treated with Tafamidis free acid 61 mg.”

Secondary objective 3 variables:

- Demographic variables (section 8.2.1)
- Age of onset of symptoms and at diagnosis (8.2.2)

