9. RESEARCH METHODS

9.1. Study design

Retrospective, multicenter, non-interventional, observational and descriptive study.

It will by no means interfere with the investigator's decision on the most appropriate medical care or treatment for the patient or carrier.

The variables collected are consistent with the objectives of the study and will be described in more detail in Section 9.3:

Primary objective	Primary variables
To determine the efficacy of tafamidis free acid 61 mg in ATTRv patients with neurologic involvement included in studies B3461028 and/or LTE (B3461045) in Spain through changes in the NIS scale at 12 months.	Neuropathy Impairment Score (NIS)
Secondary objectives	Secondary variables
To determine the efficacy of tafamidis 61 mg in ATTRv patients with neurologic involvement included in studies B3461028 and/or LTE (B3461045) in Spain using additional non-cardiac variables at 6, 12, 18, 24 and 36 months after the start of treatment.	
 - NIS at 6, 18, 24 and 36 months - NIS-LL, Norfolk QoL-DN, COMPASS-31 and FAP-RODs, FAP - % of patients who do not have stage progression in the PND score

PFIZER CONFIDENTIAL

	
 - % of patients responding to treatment (defined as <4p in NIS and <2p in NIS-LL) - R-R Range Variability - mBMI - Amplitude of the potentials measured in sural sensory and ulnar, tibial and peroneal motor NCS

To determine the efficacy of tafamidis free acid 61 mg in ATTRwt patients with neurological symptoms included in studies B3461028 and/or LTE (B3461045) in Spain, through non-cardiac variables at 6, 12, 18, 24 and 36 months after treatment initiation.
	
 - NIS, NIS-LL, Norfolk QoL-DN, COMPASS-31 and FAP-RODs, FAP - % of patients who do not have stage progression in the PND score - % of patients responding to treatment (defined as <4p in NIS and <2p in NIS-LL) - R-R Range Variability - mBMI. - Amplitude of the potentials measured in sural sensory and ulnar, tibial and peroneal motor NCS

To describe the extra-cardiac characteristics of ATTRv and ATTRwt patients included in studies B3461028 and/or LTE (B3461045) in Spain with mixed phenotype treated with tafamidis free acid 61 mg.
	
 - Demographic variables - Age of onset symptoms and at diagnosis - Neurological and extra-cardiac clinical variables

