6 METHODS FOR THE STATISTICAL ANALYSIS

The analysis methods to be used to achieve the study objectives and draw up the descriptive content for the variables are detailed below.

❖ UNIVARIATE ANALYSIS

Quantitative variables will be described with centralization and scattering measures (mean, SD (standard deviation), median, minimum, maximum, Q1 (first quartile), Q3 (third quartile and N).

Qualitative variables will be described by absolute and relative frequencies. Two columns of percentages will be presented: Total Percentage (Total %) and Valid Percentage (Valid %):

- Total Percentage (%): Percentage of the sum of valid responses plus missing values, i.e. of the total of the sample under study.
- Valid percentage (Valid %): Percentage of total valid responses, i.e. with data on the variable.

In subgroup analyses, only the valid % with respect to the total for each group will be presented.

For questions with more than one answer option, **multiple response** tables will be shown. Two percentage column will be shown in these tables:

- Total percentage (%) Percentage of the sum of valid responses plus missing values, i.e. of the total of the sample under study. Since it is multiple choice, the sum of percentages does not have to be 100 (the percentage may be exceeded).
- Valid percentage (%) Percentage of the number of patients with at least one given answer from among the possible answers. Since it is multiple choice, the sum of percentages does not have to be 100 (the percentage may be exceeded).

Missing data will not be attributed and will be left as lost data.

Statistical analysis of variables collected in the study will be performed using the SPSS statistical program.

NOTE 1: Due to the small number of patients available in the study, no comparisons will be made and the associated p-value will not be shown. Only descriptive analyses will be presented.

NOTE 2: The texts collected in open fields will not be grouped, other than to standardize format and spelling. If desired, any grouping must be performed by the sponsor and as an additional table to the description of what is included in the database.

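### The composite responder rule in SAP 12.2.1 sets patients already known to have failed one scale to missing, so they leave the ATTRv denominator and the reported rate can fall outside what the data allow

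*SAP*

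**What the plan says.** Protocol 9.1 has one responder definition, a composite used as a secondary variable in both genotypes: the percentage "of patients responding to treatment (defined as <4p in NIS and <2p in NIS-LL" points. SAP 12.2.1 carries it into the ATTRv objective with cut-offs for each month. The Month 12 rule is "change at 12 months from baseline (<4p in NIS and <2p in NIS-LL" points, and each monthly line requires the two conditions to hold simultaneously.

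Two sentences then classify everyone else. The first is "patients who do not meet the previous two conditions in each month will be considered non-responders". The second is "If complete data is not available (NIS and NIS-LL), the value will be left as missing". Neither says what happens when one scale is absent and the other has already reached its cut-off.

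SAP section 6 sets the denominators. The total percentage is the "Percentage of the sum of valid responses plus missing values, i.e. of the total of the sample under study". The valid percentage is the "Percentage of total valid responses, i.e. with data on the variable". For subgroups: "In subgroup analyses, only the valid % with respect to the total for each group will be presented". Section 6 also states the general policy: "Missing data will not be attributed and will be left as lost data".

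SAP 12.2.2 repeats the composite for ATTRwt but gives no missing-data rule for it.

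**The concern.** A composite joined by *and* can be decided by one component. If NIS has worsened by 4 points or more at Month 12, the patient is a non-responder whatever NIS-LL would have shown, and the same holds for NIS-LL worsening of 2 points or more with NIS absent. On its natural reading, the completeness sentence discards that knowledge. Counting such a patient as a failure is not imputation, so the general policy of leaving missing data alone does not require the loss.

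The result is also inconsistent between tables. With NIS failed and NIS-LL absent, the same patient at the same month is a non-responder in the NIS table of 12.2.1 and missing in the composite table. At stake is the protocol's own responder endpoint in a group of about 10, where one patient visibly moves the percentage.

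**Working it through.** The documents state no response rate, so there is no figure to reproduce.

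**Inputs.** N = 10 ATTRv patients (SAP section 4). The classification and denominator rules are those of SAP 12.2.1 and section 6. The following counts are assumptions:
- R: responders, with both scales available
- C: patients with both scales available
- F: one scale absent, the available one fails
- U: one scale absent, the available one passes

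Every patient is assumed to have at least one scale at the month, so N = C + F + U.

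**Formulas.**
- SAP valid percentage: R/C
- Rate with known failures counted: R/(C+F)
- Range the observed data allow: R/N to (R+U)/N

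**Step 1: direction against the rate that counts known failures.** R/C − R/(C+F) = R·F / [C(C+F)]. This is never negative, and it is positive when R > 0 and F > 0.

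**Step 2: size with U = 0.** The rate with known failures counted is then R/10. The SAP rate is R/(10 − F):

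| R | R/10 | F = 1 | F = 2 | F = 3 |
|---|---|---|---|---|
| 3 | 30.0% | 3/9 = 33.3% | 3/8 = 37.5% | 3/7 = 42.9% |
| 5 | 50.0% | 5/9 = 55.6% | 5/8 = 62.5% | 5/7 = 71.4% |
| 6 | 60.0% | 6/9 = 66.7% | 6/8 = 75.0% | 6/7 = 85.7% |
| 7 | 70.0% | 7/9 = 77.8% | 7/8 = 87.5% | 7/7 = 100% |

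With R = 5 the steps are 5.6, 6.9 and 8.9 points. They are smaller with R = 3 (3.3 to 5.4) and larger with R = 7 (7.8 to 12.5). With U = 0 the composite is fully determined, so every SAP figure in the F columns is one the data rule out.

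**Step 3: with undetermined patients.** Take R = 5, F = 1, U = 2, so C = 7. The SAP rate is 5/7 = 71.4%. The rate with the known failure counted is 5/8 = 62.5%. The data allow 5/10 = 50% to 7/10 = 70%, so the SAP figure lies above the upper limit.

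**Step 4: direction against the full-data rate.** Assume NIS is always seen, a true composite rate of 50%, NIS failure in 40%, and NIS-LL absent with probability 20% in the patients named:
- Absent at random in all patients: the SAP rate is 50.0%, unbiased. Counting only the known failures and leaving the rest missing gives 0.5 × 0.8 / (0.8 + 0.2 × 0.4) = 0.40/0.88 = 45.5%.
- Absent only in NIS failures: the SAP rate is 0.5 / (0.6 + 0.4 × 0.8) = 0.50/0.92 = 54.3%.
- Absent only in NIS passes: the SAP rate is 0.5 × 0.8 / (0.6 × 0.8 + 0.4) = 0.40/0.88 = 45.5%.

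A counterexample that does contain a known failure: R = 4, C = 7, F = 1, U = 2, with both undetermined patients truly responders. The truth is 6/10 = 60%, the SAP gives 4/7 = 57.1%, and counting only the known failure gives 4/8 = 50%. The bounds are 40% to 60% and contain the truth.

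**The case against.** A reader might infer that the rule can only inflate the response rate, since an incomplete patient can be a certain failure but never a certain responder. The documents do not support that. The same sentence also drops patients whose available scale passes, some of whom would be responders. As Step 4 shows, the SAP rate may be too high, too low or unbiased, depending on why a scale is absent. This part of the objection stands. It also means that reclassifying known failures, with nothing more, would replace one bias with another.

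The situation may also be rare. SAP section 5 checks that both scales are available at baseline, and section 6.1.1 fills months by a linear rate or by LVCF once a scale has a follow-up value. The gap therefore mainly needs a patient followed on one scale with little or nothing on the other. That lowers the likely count but does not remove it. No check requires both scales at follow-up, reassignment is done variable by variable, and Protocol 9.9 names scarce follow-up data as a limitation. The documents do not say how often one scale is recorded alone.

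The failure is also partly visible elsewhere, in the separate NIS and NIS-LL responder tables and the per-patient NIS listing (SAP 10.3.1). That helps a careful reader but does not correct the composite percentage.

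Finally, the non-responder sentence might be read as requiring failure on both scales, which would make a patient failing only one a responder. That reading is strained, because every composite line requires both conditions simultaneously. It is a wording point only.

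**Conclusion.** The point holds in a limited form. As written, the composite in SAP 12.2.1 discards non-responses that are logically certain, and the subgroup denominator rule then removes those patients from the ATTRv percentage. The reported rate is never below the rate that counts them, exceeds it when at least one is dropped and at least one patient responds, and can lie outside the range the observed data permit. With 10 patients and 5 responders the effect is about 6 to 9 points per such patient. It is zero if there are none.

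No fixed direction of bias against the full-data rate can be claimed. The conclusion rests on two readings: that the completeness sentence prevails when one scale is absent, and that valid percentage carries its section 6 definition in subgroups. The endpoint is secondary and descriptive, and the primary Month 12 NIS analysis and its single-scale responder rule are untouched.

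**What to change.** In SAP 12.2.1, replace the two classification sentences for the composite with a three-way rule:
- Non-responder if either available component reaches or exceeds its cut-off.
- Responder only if both components are available and both are below their cut-offs.
- Otherwise undetermined.

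At each month report R, the number of known failures with one scale absent (F) and the number undetermined (U). Give the response rate as the bounds R/N to (R+U)/N, where N is all patients with at least one scale at that month, in place of a single valid percentage. When U = 0 the bounds collapse to one figure. The bounds are valid whatever the reason a scale is absent, which is why they should accompany the reclassification.

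Apply the same rule in 12.2.2, which now has none, and to the Month 36 line under NIS-LL in 12.2.1 for as long as that line repeats the composite.

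The cost is a few sentences, a few extra table cells and a small programming change. The rate may look less favourable, and it will be a range when some patients are undetermined.
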